4. OBJECTIVES AND OUTCOME MEASURES

Objectives	Outcome Measures	
Primary objective		
To describe the frequency of LUS abnormalities consistent with pulmonary oedema	Frequency endpoint: proportion of patients with LUS consistent with pulmonary edema Severity endpoint: LUS aeration score (numerical 0 to 36)	
To describe the timing and entity of edema resolution after delivery	Frequency endpoint: Fraction of patients with improvement or resolution of LUS findings. Quantitative endpoint: delta LUS score between T1 and T2	
Secondary objectives: To describe the frequency of acute respiratory failure in patients with Severe Pre- eclampsia and in patients with Eclampsia	Proportion of patients with acute respiratory failure (see definition)	
Frequency of other LUS findings	 Proportion of patients with: consolidations isolated pleural effusion minor LUS findings Calculation of the LUS ARDS score 	
Frequency of organ support strategies	Fraction of patients that receive: - oxygen - CPAP - Mechanical ventilation	
Frequency of patients with abnormal cardiac function	Defined as either low cardiac output measured by ultrasound	
Oxygenation assessment	SpO ₂ to FiO ₂ ratio	
Frequency of Major Direct Obstetric Complications	Fraction of patients with at least one additional MDOC (APH, PPH, sepsis, uterine rupture, obstructed labour)	
Frequency of Indirect Obstetric complications	Fraction of patients with at least one among stroke, severe malaria, acute kidney injury and cardiac insufficiency	
Frequency of perinatal complications	IUFD, Apgar score, Admission to special care baby unit (SCBU)	

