5. STUDY DESIGN

This will be a single centre, prospective, cohort study of patients with severe pre-eclampsia and eclampsia. The expected duration of study is 1 year. All patients with suspected severe pre-eclampsia or eclampsia will undergo screening upon admission to HDU and the Eclamptic ward. Eligible patients will undergo a systematic clinical and LUS examination, straight after admission (**before delivery**). Clinical examination will focus on signs of respiratory, neurologic and cardiac failure. Lung ultrasound will be performed using a MyLab[™]Five ultrasound machine (Esaote Spa, Genova, Italy) and a low frequency (2.5–5 MHz) convex probe or a Butterfly ultrasound probe (Butterfly, USA). Lung ultrasound will be performed using the

validated 12-region method, evaluating 2 anterior regions, 2 lateral regions and 2 posterior in each hemithorax (18,28,29). As heart failure is a common finding in preeclamptic women, echocardiography performed with a cardiac sector probe, will enable real-time assessment of maternal cardiac contractility and cardiac output. The same clinical, LUS and echocardiographic assessment will be repeated between 24 h to 72 h (after delivery). Whenever the pre-delivery timepoint is not feasible due to late arrival, emergency scenario or postpartum onset, the after delivery examination only will be performed.

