6.4. Case definitions

Acute respiratory failure defined as RR≥30 breaths per minute AND/OR SpO₂/fraction of inspired oxygen (FiO₂) \leq 315 AND/OR signs of difficult breathing, including the use of accessory muscles or nasal flaring. FiO₂ will be derived from the amount of oxygen the patient receives in liters.

Clinical pulmonary oedema

Defined as respiratory distress (respiratory rate >30 breaths/min and/or SpO2 <92% on room air) with bilateral fine crepitations on chest auscultation.

Lung ultrasound consistent with pulmonary oedema (categorical)

The presence of three or more B-lines (any size and any distance apart) in a particular lung region will define a positive lung region for interstitial syndrome (30) Pulmonary edema will be defined as the presence of \geq 2 positive regions per side.

Abnormal lung ultrasound aeration score

The LUS aeration score (numerical) will be calculated: each lung field will be scored from 0 to 3 as follows: "0," A-pattern with \leq 2 B-lines; "1," more than 2 separated B-lines; "2," multiple coalescent B-lines; or "3," lung consolidation, defined as anechoic or tissue-like images arising from the pleural line that is limited in depth by an irregular border. A global LUS score will be calculated at each time point and ranged from 0 to 36.

LUS ARDS score

The three variables included in the final logistic regression model for diagnosis of ARDS are: left LUS aeration score (range 0-18), right LUS aeration score (range 0-18), and the number of antero-lateral lung regions with an abnormal pleural line (range 0-8). The LUS-ARDS score can range from 0 to 91 and is computed with the formula below. (31)

LUS-ARDS score = 2.5 x left LUS aeration score + 1 x right LUS aeration score + 3.5 x no. of anterolateral regions with an abnormal pleural line

Acute Respiratory Distress Syndrome (ARDS)

Defined according to the Berlin Definition or Kigali Modification as shown in **Table 1**.

Criteria	Berlin definition of ARDS	Kigali modification
Timing	Within 1 week of a known clinical insult, or new or worsening respiratory symptoms	
Oxygenation	PaO ₂ /FIO ₂ ≤300 mmHg SpO ₂ /FIO ₂ ≤315 mmHg	
PEEP requirement	Minimum 5 cm H ₂ O PEEP required by invasive mechanical ventilation (non-invasive acceptable for mild ARDS)	No PEEP requirement, consistent with AECC definition

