10. STATISTICS AND ANALYSIS

For descriptive purposes continuous and ordinal variables data will be expressed as median with interquartile range. For categorical variables, percentages are calculated. Student's t-test or analysis of

variance (ANOVA) will be used to compare normally distributed numerical variables. Mann Whitney Utests and Kruskal-Wallis tests will be used to compare numerical variables when normality cannot be assumed, while chi-squared tests will be used to compare categorical variables. Univariate logistic regression analyses will be performed to identify potential factors associated with the clinical outcomes including, but not limited to, presence of interstitial syndrome, non-resolution of interstitial syndrome at 48-72h, development of ARDS and death in hospital. Multivariable logistic regression models will be used to identify independent risk factors for the same clinical outcomes. A forward and backwards stepwise approach will used to include variables into the models, with a limit of P <0.2.

Inter– observer variability of the lung ultrasound score between the study sonographer and an independent expert will be calculated on a random sample of 10 cases (120 lung regions) using Cohen K-statistics. Statistical analyses will be conducted using R (www.r-project.org). A P-value of <0.05 will be considered statistically significant. Analyses will be conducted after the end of patient recruitment and no interim analyses are planned. Statistical analysis will be performed with R software (R Foundation for Statistical Computing, Vienna, Austria).

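### Adjustment for the pre-delivery (T1) LUS score is not guaranteed in the multivariable non-resolution model, nor in any group comparison of delta LUS

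*Combined protocol and SAP*

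**What the plan says.** Resolution after delivery is part of the primary objective. Section 4 gives it two measures: "Fraction of patients with improvement or resolution of LUS findings" and "Quantitative endpoint: delta LUS score between T1 and T2". The documents do not define T1 and T2; I read them as the pre-delivery and post-delivery scans of Section 5. Under Section 6.4 the score is bounded: "A global LUS score will be calculated at each time point and ranged from 0 to 36". The same section sets the categorical threshold: "Pulmonary edema will be defined as the presence of" at least two positive regions on each side.

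Section 10 supplies three kinds of analysis that could bear on resolution:

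- **Generic comparisons.** These are t-test or ANOVA under normality; otherwise Mann-Whitney and "Kruskal-Wallis tests will be used to compare numerical variables when normality cannot be assumed". Neither delta LUS nor a grouping factor is named.
- **Univariate logistic regression** for outcomes that include "non-resolution of interstitial syndrome at 48-72h, development of ARDS and death in hospital".
- **Multivariable logistic regression** for the same outcomes, to find independent risk factors, with stepwise entry at P<0.2. No candidate covariates are listed and none is forced in.

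The T1 score is not mentioned as a covariate or stratifier, and no analysis of covariance or repeated-measures model is planned. Section 5 also allows some women to have no T1 score: where a pre-delivery scan is not feasible, "the after delivery examination only will be performed".

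**The concern.** How far a bounded score can fall, and whether it drops below the oedema threshold by T2, both depend on where it started. Take a factor that goes with a higher T1 score but leaves clearance unchanged. Women with the factor have more to lose, so their mean fall is larger. They also start further above the threshold, so more of them are still above it at T2. Without T1 in the analysis, the same factor can be reported as a sign of greater improvement and as a risk factor for non-resolution, although it tells us nothing about clearance.

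This matters most for the multivariable model, because that is where the plan promises independent risk factors. If T1 is absent, the word independent is not earned with respect to starting severity, the strongest obvious confounder.

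**Working it through.** The documents state no sample size, SD, T1 gap or clearance, so there is no figure of theirs to reproduce. Two simulation settings with assumed inputs show direction and rough size. In both, the factor has no effect on T2 once T1 is known, so every rejection at two-sided 0.05 is false. Both use a score cut-off in place of the regional definition. The lowest score compatible with that definition is 2 regions x 2 sides x 1 point = 4.

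**Setting A (assumed).** 30 v 30 women positive at T1, T1 SD 5, half the score cleared, noise SD 2.5, non-resolution taken as T2 score >=6, 2000 datasets.

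- Expected spurious difference in delta for means of 10 v 14: (1 - 0.5) x 4 = 2.0 points. Simulated mean change: -5.1 v -7.0, a difference of 1.9.
- Non-resolution: 45% v 66%, odds ratio (0.66/0.34)/(0.45/0.55) = 1.94/0.82 = 2.4.

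| T1 gap | Mann-Whitney on delta | Non-resolution, unadjusted | T2 on group + T1 | Logistic + T1 |
|---|---|---|---|---|
| 2 points | 18% | 14% | 4.5% | 4.1% |
| 4 points | 54% | 40% | 4.9% | 4.5% |

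Repeat runs of this design, with changes in score handling (for example a T1 floor of 4, or a cut-off of 4 instead of 6), gave 46-57% for delta and 27-40% for non-resolution at the 4-point gap. At the 2-point gap non-resolution was 10-15%. Both misleading results were significant together in 15-22% of datasets at the 4-point gap. With no gap, rates were about 5%.

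**Setting B (assumed).** N = 100 or 200 in two roughly equal groups, overall T1 mean 10, SD 6, T2 = 1 + b x T1 + error (SD 3), scores rounded and limited to 0-36. Delta uses all women; non-resolution uses women with T1 score >=6. 1000 datasets per cell.

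Analytic check for delta: spurious difference = (1 - b) x d, with SD = sqrt(((1 - b) x 6)^2 + 3^2). For b = 0.4, d = 4 and 50 per group:

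- difference = 0.6 x 4 = 2.4
- SD = sqrt(12.96 + 9) = 4.69
- standard error = 4.69 x sqrt(2/50) = 0.94
- rejection is about Phi(2.4/0.937 - 1.96) = Phi(0.60) = 0.73 (simulated 0.75)

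| Gap d | N | Delta, t-test (b = 0.4 to 0.8) | Non-resolution, unadjusted | Median unadjusted OR |
|---|---|---|---|---|
| 2 | 100 | 24% to 12% | 3-6% | 1.21-1.28 |
| 2 | 200 | 43% to 15% | 7-10% | 1.23-1.31 |
| 4 | 100 | 75% to 26% | 8-14% | 1.49-1.79 |
| 4 | 200 | 96% to 47% | 17-25% | 1.51-1.76 |

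With T1 as a covariate, rejection is 3.9-6.2% for delta and 3.1-6.5% for non-resolution, and the median adjusted odds ratio is 0.95-1.03. Both misleading results occur together in at most 10% (N = 100) or 23% (N = 200).

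**What stepwise selection would do.** In Setting A with a T1 floor of 4, T1 and group were both offered at P<0.2 (1000 datasets per gap). T1 was retained in 99.9% (4-point gap) and 100% (2-point gap). The group factor was then falsely significant in 4.9% and 3.7%, against 39% and 15% unadjusted. The protection therefore depends on T1 being on the candidate list, which Section 10 does not settle.

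**The case against.** The strongest reply has four parts.

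1. **Stepwise selection may already adjust for T1.** This stands if T1 is offered. A reader might infer that the planned non-resolution models omit T1; the documents do not support that. They leave candidates unlisted, so all that can be said is that T1 is neither named nor guaranteed.
2. **No group test of delta LUS is planned by name.** This also stands. A reader might infer such a test from the generic list, but Section 4 uses delta to describe the cohort and Section 5.1 calls the study explorative and descriptive. A whole-cohort summary of delta needs no T1 adjustment. The concern about delta applies only if Section 10's tests are turned on it.
3. **Univariate results are legitimate.** They show who still has interstitial syndrome at T2, and Section 10 says only that they find potential factors. If a factor acts through severity at T1, then T1 is a mediator and adjustment removes part of the total association. So it would be wrong to call the univariate models invalid or to require T1 in each of them.
4. **The sizes are assumed.** True. A 4-point gap is 0.8 SD in Setting A, nothing in the documents ties eclampsia or any other factor to higher T1 scores, and with no gap there is no distortion. For non-resolution in Setting B at N = 100, the excess over 5% is small.

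What survives is the multivariable model. It claims independence, yet adjustment for starting severity is left to an unlisted candidate set and a P-value rule.

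**Conclusion.** The concern holds in a limited form. Section 10 does not guarantee T1 adjustment in the multivariable non-resolution model, and its generic tests would leave any group comparison of delta LUS unadjusted. A factor tied only to T1 severity could then be misreported in two opposite directions.

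The direction follows from the bounded score and partial clearance. The size rests wholly on assumed T1 gap, clearance, SD and N: at 30 v 30, roughly 10-18% false positives for a 2-point gap and 27-57% for a 4-point gap. Setting B gives 3-25% for non-resolution across N = 100 and 200. All return to about 5% with T1 included. These are illustrations, not bounds, and error in measuring T1 would leave some residual bias even after adjustment.

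This is a cheap improvement to a secondary modelling step. It does not undermine the descriptive primary endpoints.

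**What to change.** Amend Section 10 as follows.

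- Define the non-resolution analysis set as women LUS-positive at T1 who have a T2 scan. State the T2 window for it, since Section 5 gives 24 to 72 h and Section 10 gives 48-72 h; these need to be reconciled.
- Force the T1 LUS score into the multivariable non-resolution model, outside stepwise selection.
- For any group comparison of change, regress the T2 score on group and T1 score (linear with robust errors, or proportional odds) in place of a raw test on delta.
- Keep the univariate models, labelled as unadjusted associations with persisting oedema, and keep raw delta LUS as the descriptive endpoint.
- Report how many women had no pre-delivery scan and so fall outside these analyses.

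The cost is SAP wording and one degree of freedom per model, on data already collected. The adjusted estimate leaves out any effect that acts through T1 severity; the unadjusted estimate, reported beside it, includes that effect.

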Respiratory distress and pulmonary oedema are known complications of preeclampsia-eclampsia and their insurgence is a hallmark of severe disease (7,8). Pulmonary oedema is reported as a complication in 2.9% of patients with preeclampsia-eclampsia (9). Pulmonary involvement is associated with worse maternal and perinatal outcomes (10,11). Incidence is significantly higher in low income countries, rising to 12% due to poorer prenatal care and access to hospital care, and suboptimal diagnostic and management processes (12).

A retrospective study showed how the average time to resolution of pulmonary oedema for obstetric patients with different primary clinical disorders was 2.4 days (13). The preeclamptic and eclamptic patients is characterized by systemic endothelial cell dysfunction, increased systemic vascular resistance and increased capillary permeability, all leading to excessive extravasation and as such increasing the risk of pulmonary oedema (14,15). This is also why, together with the infectious cause, preeclampsia/eclampsia are the leading cause of ARDS in pregnancy (16,17).

Challenges with diagnosis and follow up of pulmonary complications

In the absence of imaging modalities (chest radiography, computed tomography) and laboratory measures (blood gas analysis) it may be difficult to quantify respiratory deterioration, or the pulmonary component in a global deterioration. Bedside clinical examination lacks sufficient sensitivity and specificity for

pulmonary edema and ARDS. Simple bedside techniques are increasingly available, such as pulse oximetry for quantification of oxygenation deficit and lung ultrasound for systemic imaging.

Use of lung ultrasound to detect pulmonary complications

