5.1. Sample size calculation

There is very limited data on the prevalence of pulmonary edema in eclampsia patients. For this explorative descriptive study we plan to recruit all eligible patients during a 12 months study period.

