Chest imaging	Bilateral opacities not fully explained by effusions, lobar/lung collapse, or nodules by chest radiograph or CT	Bilateral opacities not fully explained by effusions, lobar/lung collapse, or nodules by chest radiograph or ultrasound
Origin of oedema	Respiratory failure not fully explained by cardiac failure or fluid overload (need objective assessment, such as echocardiography, to exclude hydrostatic oedema if no risk factor present)	

Table 1. Berlin Criteria for ARDS and Kigali Modification of the Berlin Criteria (19,32)

Bilateral opacities on ultrasound will be defined as two or more regions with a B-pattern and/or C-patterns per hemithorax bilaterally (33).

Abbreviations: ARDS, acute respiratory distress syndrome; PaO2, arterial oxygen tension; FiO₂, fraction of inspired oxygen; SpO₂, oxygen saturation as measured by pulse oximetry; AECC, American-European Consensus Conference; CT, computed tomography; PEEP, positive end-expiratory pressure.

Abnormal cardiac function

Defined as a cardiac index (CI) <2.5 l/min/m2 measured by echocardiography.

Modified Early Warning (MEWS) Score

The modified early warning score ranges from 0 to 14 and is calculated as detailed in **Table 2** (34) (35).

Physiological parameters	Normal values (0 points)	Yellow alert (1 point)	Red Alert (2 points)
Respirator rate	10- 20 breaths pwe minute	21- 30 breaths per minute	<10 or >30 breaths per minutes
Oxygen saturation	96- 100%		<95%
Temperature	36.0- 37.4°C	35- 36 or 37.5- 38°C	<35 or >38°C
Systolic blood	100- 139 mmHg	150- 180 or 90- 100	>180 or < 90 mmHg
pressure		mmHg	
Diastolic blood	50- 89mmHg	90- 100 mmHg	>100 mmHg
pressure			
Heart rate	50- 99 beats per		>120 or <40 beats per minutes
	minute	100- 120 or 40- 50	
		beats per minute	
Neurological	Alert	Voice	Unresponsive, pain
response			

Table 2. The Modified Early Warning Score score.

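### Stepwise selection at P<0.2 from an unnamed, unlimited candidate set invalidates the P values of the risk-factor models and makes chance findings likely

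*Combined protocol and SAP*

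**What the plan says.** Section 10 plans univariate and then multivariable logistic regression. The purpose of the second step is explicit: "Multivariable logistic regression models will be used to identify independent risk factors for the same clinical outcomes". The named outcomes are "presence of interstitial syndrome, non-resolution of interstitial syndrome at 48-72h, development of ARDS and death in hospital", and the list is left open by the words "potential factors associated with the clinical outcomes including, but not limited to". Variables are chosen as follows: "A forward and backwards stepwise approach will used to include variables into the models, with a limit of P <0.2". The significance rule is "A P-value of <0.05 will be considered statistically significant".

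Section 10 gives no list of candidate variables, no limit on variables per event, no penalisation, no internal validation, no multiplicity adjustment and no exploratory label on these models. It does not say whether 0.2 governs entry, removal or both.

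The sample size section gives no number: "For this explorative descriptive study we plan to recruit all eligible patients during a 12 months study period". Identifying risk factors is not among the objectives in Section 4.

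**The concern.** A standard P value assumes that the model was fixed before the data were seen. Here the data choose the model, and the same data then supply the P values and confidence intervals. Neither is corrected for the choice, so a survivor at P<0.05 does not carry a 5% error rate. Its odds ratio is also biased away from 1, because only variables that look large enough are kept.

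Without a candidate list, the number of variables that get a chance to appear is unknown and unlimited. The label of independent risk factor invites readers to treat the survivors as established.

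There is a separate problem for ARDS. Nothing keeps the measurements that define the diagnosis out of the model for that diagnosis.

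At stake is the credibility of the risk-factor tables for interstitial syndrome, non-resolution, ARDS and death. The frequency and resolution estimates that form the primary aim do not depend on these models.

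**Working it through.** The plan has no figure to reproduce: it states no N, event count, power or number of candidates. The calculations below therefore use assumed ranges (N 100–400, 6–80 events, 10–20 candidates), with every candidate unrelated to the outcome.

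**1. Theory, K independent noise candidates**

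- Expected number passing 0.2 is 0.2K: 2 for K=10 and 3 for K=15.
- Chance that at least one passes 0.2 is 1 − 0.8^K: 89% for K=10 and 96% for K=15.
- Chance that at least one passes 0.05 with no selection is 1 − 0.95^K: 40% for K=10 and 54% for K=15.
- A noise variable that has already passed 0.2 has P<0.05 with probability about 0.05/0.20 = 25%. The nominal rate is 5%. This is the sense in which the P values after selection are invalid.

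**2. Simulated stepwise logistic regression**

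Half the candidates were continuous and half binary. A variable entered on likelihood-ratio P<0.2 and left on Wald P≥0.2. There were 300 runs per row, with a simulation error of about 3 points in the last column.

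| N | Events | Candidates | Mean noise variables kept | At least one kept | At least one at P<0.05 |
|---|---|---|---|---|---|
| 200 | 40 | 10 | 1.96 | 87.0% | 41.0% |
| 200 | 40 | 15 | 3.05 | 96.7% | 58.3% |
| 200 | 80 | 10 | 1.98 | 88.7% | 45.3% |
| 200 | 80 | 15 | 3.20 | 97.3% | 61.0% |
| 400 | 12 | 10 | 1.76 | 78.7% | 33.3% |
| 400 | 12 | 15 | 2.53 | 88.3% | 39.3% |
| 400 | 48 | 10 | 2.09 | 89.0% | 40.0% |
| 400 | 48 | 15 | 2.98 | 96.7% | 50.3% |

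Other runs at N=200 with 20 events gave 42–43% (10 candidates) and 54–59% (15 candidates). N=300 with 15 events and 15 candidates gave 54%. Over all settings with 12–80 events and 10–20 candidates the range is 27–74%. With 6 events it is 23–45%, where Wald tests are conservative.

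**3. What drives the per-model rate**

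In a further pure-noise run, stepwise models held a P<0.05 factor in 45–63% of cases. Full models with all candidates and no selection did so in 42–63%. The number of candidates therefore drives this rate, and selection adds little to it. What selection does is discard the non-significant variables and report the rest at face value: 26–31% of the kept noise variables had P<0.05, close to the 25% in step 1.

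By contrast, 1–4 prespecified covariates with no selection at N=200 gave at least one false P<0.05 in 5–12% of models (6 events), 6–18% (24 events) and 6–16% (40 events).

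**4. What few events do**

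For a continuous noise variable, the SE of the log odds ratio per SD is about 1/√(N·q·(1−q)), with q the event rate. Given |z|>1.96, the median |z| is 2.24.

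- N=200, 20 events: SE = 1/√18 = 0.236; exp(2.24 × 0.236) = 1.70.
- N=300, 15 events: SE = 1/√14.25 = 0.265; exp(2.24 × 0.265) = 1.81.

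Simulation gives about 1.8 for noise factors that reach P<0.05. Among all kept binary noise factors (N=200, 10 candidates), the median odds ratio, taken away from 1, was 3.5, 2.3 and 2.0 with 12, 24 and 40 events.

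**5. Event counts that the documents' rates would imply**

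| Rate and source | N=100 | N=200 | N=400 |
|---|---|---|---|
| 1.36%, national maternal mortality (3.1) | 1.4 | 2.7 | 5.4 |
| 2.9%, pulmonary oedema (3.1) | 2.9 | 5.8 | 11.6 |
| 12%, pulmonary oedema in low-income countries (3.1) | 12 | 24 | 48 |
| 20%, hypothesised floor for LUS oedema before delivery (4.1) | 20 | 40 | 80 |

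None of these is a rate of death, ARDS or non-resolution in this cohort; they only show the order of magnitude.

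**6. Overlap with the ARDS definition**

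In Section 6.4 the Kigali criteria use SpO2/FiO2 ≤315 and accept bilateral opacities on ultrasound, defined as "two or more regions with a B-pattern and/or C-patterns per hemithorax bilaterally". Section 13.7.1 says no other lung imaging is available on site, so LUS will in practice supply the imaging criterion. LUS pulmonary oedema needs at least two positive regions per side, which is nearly the same rule. Values from the assessment that makes the diagnosis therefore predict it by construction.

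**The case against.** **The false-positive rate is not due to stepwise selection.** Testing 10 or 15 noise variables without selection gives 40% or 54%, within simulation error of most of the stepwise results. This stands, and the candidate count is itself an assumption. It does not rescue the plan, because Section 10 leaves that count unlimited and the P values reported after selection remain uncorrected.

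**A survivor need not be called significant.** The separate 0.05 threshold means that a variable kept at P between 0.05 and 0.2 may be shown without a claim. This also stands, which is why the size is stated at P<0.05.

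**The study calls itself exploratory and descriptive, and risk factors are not an objective.** That limits the stakes. But the wording sits in the sample size section, while Section 10 attaches a significance rule and the independent-risk-factor label to these models.

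**The ARDS overlap is speculative.** No text lists LUS or SpO2/FiO2 as candidates, and the outcome is development of ARDS, for which an earlier scan is a legitimate predictor. This stands in part: the problem is confined to values from the diagnosing assessment.

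**Events-per-variable limits and the choice of penalty are conventions.** Agreed. The remedy should state the principle and leave the exact cut-off to the study statistician.

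**Conclusion.** The concern holds. The selection rule gives P values and confidence intervals that are not valid as stated, and chance associations are likely. With 10–15 noise candidates, roughly 40–60% of final models hold at least one P<0.05 factor, fewer when events are about 12 or below, and 2–3 noise variables are usually kept. The figures assume independent candidates with no true effect, and N, event counts and candidate numbers that the plan does not supply.

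A reader might infer more than the documents support:

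- *That false risk factors will be reported, or will appear in more than half of the models.* The first is too certain. The second holds at about 15 candidates but not at 10.
- *That the outcomes are rare.* This is plausible for death and ARDS. No event count is given, however, and LUS oedema before delivery is hypothesised above 20%. Rarity is not needed either: false selection was as frequent with 80 events.
- *That univariate results screen variables into the multivariable model.* Section 10 lists both analyses but does not say so.
- *That triage decisions rest on these models.* Section 3.2 links triage to ultrasound assessment and to the cohort data in general, and does not mention risk-factor modelling.
- *That every LUS variable is circular for ARDS.* Only values from the diagnosing assessment are.

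**What to change.** Replace the stepwise sentence in Section 10 with a rule along these lines:

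- For each outcome, fix a short candidate list before database lock, drawn from baseline data already collected under Sections 7.4.1 and 7.4.2 (for example age, eclampsia versus severe pre-eclampsia, blood pressure and GCS). Rank the list in advance, so that the event count decides only how many of its entries are used.
- Keep all candidates in the model, with no selection by P value, and fit penalised logistic regression such as Firth or ridge.
- Where events are too few for a multivariable model, report univariable estimates with confidence intervals for the same short list only.
- Do not enter in the ARDS model the LUS or SpO2/FiO2 values from the assessment used to diagnose ARDS. Earlier values may be candidates for ARDS that develops later.
- Report associated factors, labelled exploratory, in place of independent risk factors.

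The cost is one paragraph and no new data. The downside is that fewer variables can be examined jointly.
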